Mindfulness + tDCS to reduce urgency incontinence in women

NCT# 04652869

Study Protocol 9/13/2022

Scientific background

Urinary incontinence, particularly urinary urge incontinence (UUI), is a highly prevalent and costly (\$83 billion/year) disorder among older women. Greater than 50% of UUI-related urgency and leakage may be due to situational incontinence provoked by confrontation with specific contextual triggers or cues (e.g., seeing one's front/garage door, doing dishes). We recently found that women with UUI experience increased urgency and actual leakage when exposed to personal "urge" versus "safe" photographic cues taken from their daily lives. Decades of cue-based research across other disorders has shown that such conditioned responses are rarely attenuated with pharmacologic methods and require cognitive and behavioral retraining. Therefore, new methods are needed to specifically target conditioned factors contributing to UUI, in order to effectively combat this persistent contributor to urgency and leakage and augment the efficacy of current UUI treatments.

We propose to test two new intervention methods to attenuate UUI symptomatology and reactivity to urgency cues among women with situational UUI. These methods include brief mindfulness (MI) and transcranial direct current stimulation (tDCS). Employing our well-tested method to personalize cues, women with situational UUI will create photographic personal "urge" cues, which capture their strongest urgency, and "safe" cues, in which they do not experience urge. Then, we will examine the feasibility, acceptability, participant compliance, and efficacy of using MI and/or tDCS to reduce cue-provoked urgency and/or leakage to these salient personal cues, reduce reaction time on a urinary Stroop test, and decrease multiple UUI outcomes.

Study Objectives:

Aim 1: Assess intervention feasibility, acceptability, and compliance. H1: Feasibility: 85% of all enrolled participants will complete the study, Acceptability: Moderate to high acceptability rating of ≥ 50 (0-100 scale) and Participant compliance: ≥ 75 (0-100 scale) for MI compliance on the self-reported post-study survey.

Aim 2: Examine UUI symptom reduction. H1: Each intervention will lead to a pre-post and pre-follow-up reduction in number of UUI episodes, self-report urgency, and bladder symptom severity (ICIQ-FLUTS). H2: MI + tDCS will lead to the greatest reduction in these UUI symptoms.

Aim 3: Examine attenuation of reactivity to urgency stimuli. H1: Each intervention will reduce cue-reactivity and urinary Stroop reaction time. H2: MI + tDCS will lead to greater reductions in these measures relative to either MI or tDCS alone.

Study Design and methods

We will examine the independent and combined effects of brief mindfulness (MI) and transcranial direct current stimulation (tDCS) across three group: 1) MI, 2) tDCS, 3) MI + tDCS. MI and / or tDCS will be employed during urgency-cue exposure to examine the efficacy of these methods to attenuate cue reactivity (cue-induced urgency, reaction time during a urinary Stroop test) and lead to reductions in self-reported bladder problem severity (ICIQ-FLUTS score), UUI episodes, and urgency ratings. Some participants will be trained in a brief mindfulness intervention (MI; 20-minute audio guide) to focus on body scan with acceptance language and will practice it out of session to use during cue exposure. Second, transcranial direct current stimulation (tDCS) targeting the dorsolateral prefrontal cortex (dPFC) will be used to increase cortical excitability in the dPFC, aimed at increasing cognitive control when confronted with personal urgency cues. tDCS has been shown to reduce cue reactivity on its own, and we will also test it as such, but research has also shown augmentation of its effectiveness when paired with tasks that engage brain regions being targeted for related behavior change. Past research has shown that mindfulness engages the PFC and that women with UUI who are not responsive to pharmacotherapy demonstrate down regulation of the PFC,

suggesting that tDCS combined with MI should further enhance cognitive control over reactivity to cue-provoked urgency and reduce UUI-related outcomes.

Procedures and Protocols

Sixty women will be recruited from the Pitt+Me online registry, local fliers and through collaboration with multiple community and university resources (see recruitment). Telephone screening will determine initial eligibility. Eligible participants will be invited to [name] laboratory for informed consent, further screening, and a semi-structured interview to identify personal urgency and safe cue environments, of which each participant will take pictures. Participants will then be randomized to one of 3 groups: 1) Mindfulness, 2) tDCS, 3) Mindfulness + tDCS. We will use the SAS® high quality pseudorandom deviate generator (SAS Institute, Cary, NC) to randomize subjects in a 1:1:1 ratio. We will use a blocked randomization scheme to force an approximate balance between the number of subjects in each arm at any point during recruitment. Participants will undergo 4 urgency cue exposure sessions with their assigned intervention. Cue-induced urgency and reaction time to modified Stroop will be assessed at baseline and post-training. Bladder diary and urgency survey will be completed daily throughout the study, and for one-week post-training.

Interventions:

1) Brief Mindfulness (Body Scan with awareness/acceptance language): Imaging studies have revealed enhanced activation of the PFC¹, and more specifically the dIPFC^{2,3}, during mindfulness practice, and while completing executive processing tasks after MI training. During mindfulness training, practitioners cultivate a nonjudgmental state of attention to experiences in the present moment⁴, resulting in **active engagement of attentional control abilities**⁵⁻⁷. Recent work on MI-based stress reduction (MBSR) to attenuate UUI symptoms found significant reductions in UUI episodes post-treatment, with continued reduction over 6 months post-treatment, suggesting increased benefit over time^{8,9}. Mindfulness has also been shown to reduce cue reactivity, with significant reductions in cue responding to food¹⁰, anxiety¹¹, addiction¹²⁻¹⁴, and mood regulation¹⁵ cues following MI training, presumed to reflect increased cognitive control over salient disorder-related stimuli. Recently, less intensive brief mindfulness interventions (i.e., significantly less than 8-week MBSR) have been tested with positive results.¹⁶⁻²⁰ This work has shown immediate beneficial effects on anxiety¹⁸, coping with social stressors³, acute pain²⁰ and increasing self-control,¹⁹ without requiring a full MBSR program²¹. Brief interventions are lower cost, less burdensome and more accessible at home, which is attractive for a self-management care model for chronic illness.^{22,23} Given the success in reducing UUI episodes following the full 8-week MBSR program^{8,9} UUI is a particularly good candidate for testing new brief mindfulness methods.

A component of MBSR commonly isolated for brief intervention is body scan²⁴. This method involves focused attention on the present moment through observing one's breath and bodily sensations, while becoming aware of, and accepting without judgement, any thoughts and feelings that arise.²⁵ Body scans are used for brief mindfulness training in both clinical and research protocols, and typically last between 5 and 30 min^{20,21}. We will test a novel MI presented and practiced with a 15-minute guided audio recording consisting of guidance to attend to physical sensations with a gentle, accepting attitude.

2) Transcranial Direct Current Stimulation (tDCS): tDCS is a safe, non-invasive method of brain stimulation that **can enhance cortical excitability and help attenuate cue-induced reactivity**. tDCS has become increasingly popular in clinical and neurocognitive research, showing promising efficacy for targeting cue-reactivity to stimuli related to a number of disorders (depression, addiction, anxiety), assisting physical and cognitive recovery secondary to stroke and spinal cord injury²⁶⁻²⁸, and promoting cognitive enhancement in healthy subjects.²⁹

³² Addiction research incorporating tDCS has shown reductions in cue-induced craving in response to drug-related stimuli from baseline to re-test following a single session of tDCS,³³ as well as reductions in cue-induced craving and actual smoking after 3-5 tDCS sessions.³⁴

In anxiety research, reductions in self-reported and physiological reactivity to fear stimuli have been noted after similar tDCS methods³⁵. These effects have been characterized through consideration of the PFC's role in decision-making and cognitive control and are presumed to reflect increased control over cue reactivity following PFC-targeted tDCS. Although effective as a standalone treatment to reduce reactivity, the effects of tDCS are greatly enhanced when stimulation is paired with behavioral training that engages the brain processes that underlie the targeted behavior.³⁶ Thus, we purport that brief mindfulness during urgency-cue exposure is a prime candidate for augmentation with dIPFC-targeted tDCS. Enhancement of excitability in the PFC during mindfulness, which has also been shown to increase dIPFC activation^{3,37,38} and cognitive control³⁹ should lead to greater ability to dynamically recruit cognitive control systems during urgency situations, which will aid in retraining the salience of urgency-related cues.

Inclusion Criteria:

- Ambulatory women aged 40+ years
- Able to differentiate between stress symptoms (cough, laugh, exercise) and urgency symptoms (leakage following sudden strong urge to void that is difficult to defer), and history suggestive of UUI using our detailed incontinence history questionnaires and clinical expertise.
- self-report of 2 leaks/week,
- Self-report of 'sometimes' or 'often' experiencing urgency or leakage in at least 4 of 15 common urgency trigger scenarios
- A bother score ≥ 4 on a situational urgency questionnaire
- Subjects using OAB medication will be considered if they have used it consistently for 3 months and plan to keep using it throughout the duration of the study.

Exclusion criteria:

- Inability to reliably describe incontinence type (i.e. Inability to identify situational urgency trigger scenarios, differentiate between stress and urgency incontinence, describe leakage scenarios.)
- Cognitive impairment (inability to: accurately complete a bladder diary, identify and take appropriate photos of urge cue and safe cue scenarios, appropriately give incontinence history)
- Spinal cord injury; history of pelvic irradiation, advanced uterine or bladder cancer
- Urinary retention [PVR >200 ml]
- Interstitial cystitis; artificial sphincter implant
- Medical instability or expected change in medication during the study (e.g. change in anticholinergic, diuretic medication)
- Conditions that preclude tDCS including: Epilepsy or current seizure disorder, pregnant or lactating, implanted cardiac or brain medical device.

Primary Outcomes: Data Analysis Plan. Prior to hypothesis testing, descriptive statistics and graphic displays will be used to identify outliers, missing data, and patterns of attrition, and to guide transformations and appropriate tests. The primary analyses will be evaluated via mixed model regressions with Bonferroni post-hoc comparisons. Mixed model regression features advantages over traditional regression due to the ability to handle repeated assessments of both predictor variables and outcome variables. For **Aim 1**, We will assess feasibility as $>85\%$ study

completion, acceptability as a score ≥ 50 on 8-item post-study survey rating (scale 0-100), and mindfulness compliance as an average rating ≥ 75 on the compliance survey (scale 0-100). We will use chi-square to assess attrition differences between groups, and one-way ANOVA to assess differences in acceptability and compliance ratings. For **Aim 2**, mixed model regressions will test the main effects of experimental group (1=MI, 2=tDCS, and 3=MI+tDCS) on ICIQ-FLUTS score (pre, post, and follow-up), UUI episodes, and urgency survey scores (3-day mean score at baseline, last three days before re-test, and last 3-days of follow-up) as dependent variables. Pre-intervention (baseline) levels of each dependent variable will be entered as a covariate in respective regression models. This process will be repeated for **Aim 3**, with separate models evaluating treatment effects on Stroop RT and cue-provoked urgency. For Stroop RT, the primary dependent variable will be post-test minus pre-test change. For cue-provoked urgency, the primary dependent variable will represent a double-difference score of urgency minus safe cues, and post-test minus test.

7. Malinowski P. Neural mechanisms of attentional control in mindfulness meditation. *Frontiers in neuroscience*. 2013;7:8.

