Mindfulness + tDCS to reduce urgency incontinence in women

NCT# 04652869

Primary Outcomes: Data Analysis Plan

9/13/2022

Primary Outcomes: Data Analysis Plan. Prior to hypothesis testing, descriptive statistics and graphic displays will be used to identify outliers, missing data, and patterns of attrition, and to guide transformations and appropriate tests. The primary analyses will be evaluated via mixed model regressions with Bonferroni post-hoc comparisons. Mixed model regression features advantages over traditional regression due to the ability to handle repeated assessments of both predictor variables and outcome variables. For **Aim 1**, We will assess feasibility as >85% study completion, acceptability as a score ≥ 50 on 8-item post-study survey rating (scale 0-100), and mindfulness compliance as an average rating ≥ 75 on the compliance survey (scale 0-100). We will use chi-square to assess attrition differences between groups, and one-way ANOVA to assess differences in acceptability and compliance ratings. For **Aim 2**, mixed model regressions will test the main effects of experimental group (1=MI, 2=tDCS, and 3=MI+tDCS) on ICIQ-FLUTS score (pre, post, and follow-up), UUI episodes, and urgency survey scores (3-day mean score at baseline, last three days before re-test, and last 3-days of follow-up) as dependent variables. Pre-intervention (baseline) levels of each dependent variable will be entered as a covariate in respective regression models. This process will be repeated for **Aim 3**, with separate models evaluating treatment effects on Stroop RT and cue-provoked urgency. For Stroop RT, the primary dependent variable will be post-test minus pre-test change. For cue-provoked urgency, the primary dependent variable will represent a double-difference score of urgency minus safe cues, and post-test minus test.

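### OAB medication status, known at screening, is used neither in the blocked randomisation nor in the Aim 2 models; the cost is a modest loss of precision and some chance imbalance

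*Protocol*

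**What the plan says.** Eligibility (protocol, Inclusion Criteria): "Subjects using OAB medication will be considered if they have used it consistently for 3 months and plan to keep using it throughout" the study. Women not on medication are eligible too, and the same threshold of 2 leaks per week applies to both. The exclusion criteria add "Medical instability or expected change in medication during the study (e.g. change in anticholinergic, diuretic medication").

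Allocation (protocol, Procedures and Protocols): "Sixty women will be recruited from the Pitt+Me online registry" and other sources, and the plan is to "randomize subjects in a 1:1:1 ratio". On blocking: "We will use a blocked randomization scheme to force an approximate balance between the number of subjects in each arm". No stratification factor or block size is given.

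Analysis (SAP, with the same text in the protocol's data analysis plan): the Aim 2 mixed models test experimental group on ICIQ-FLUTS, UUI episodes and urgency scores. "Pre-intervention (baseline) levels of each dependent variable will be entered as a covariate in respective regression models". No other covariate is named, and the same process is repeated for Aim 3. No analysis by medication status is described.

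On prefrontal function (protocol, Study Design and methods): "women with UUI who are not responsive to pharmacotherapy demonstrate down regulation of the PFC".

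**The concern.** The exclusion for expected medication change, with anticholinergics as an example, shows that the protocol regards bladder drugs as relevant to what it measures. Baseline medication status may therefore be prognostic for the three Aim 2 outcomes. Baseline score records how severe symptoms are now, but not whether that is severity on or off a drug. Two women with the same score may then change differently over the study.

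Blocking on arm size does nothing to balance medication use. In arms of 20 a visible gap can arise by chance. If it does, the team would be deciding whether to adjust after seeing the data. Prespecifying the term removes that choice and takes any explained variance out of the error term.

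**Working it through.** **Inputs from the documents.** 60 women, 1:1:1, so 60/3 = 20 per arm. Model terms: group and baseline outcome. The documents give no alpha, power, SD or effect size, so there is no stated figure to reproduce.

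**Assumed inputs.** Number of users M among the 60: 6 (10%), or 15 to 30 (25% to 50%). Pre-post correlation r = 0.5. Medication effect 0.5 SD, on level (L), on change (C), or on both. The documents support none of these values; they only set the scale.

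**1. Chance of imbalance.** With M users and arms of 20, the probability of i, j and k users in the three arms is C(20,i)·C(20,j)·C(20,k)/C(60,M), where i+j+k = M. Summing over the relevant cells gives:

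| Users of 60 | Some pair differs by ≥4 | A given pair differs by ≥4 | Some pair differs by ≥6 | A given pair differs by ≥6 |
|---|---|---|---|---|
| 6 | 15% | 6% | 0.2% | 0.2% |
| 15 | 40% | 20% | 10% | 4% |
| 20 | 48% | 24% | 16% | 7% |
| 25 | 51% | 27% | 19% | 8% |
| 30 | 50% | 27% | 19% | 8% |

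Four women are 4/20 = 20 percentage points.

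**2. Shift in a contrast.** After adjustment for baseline, the medication effect left over is c = L(1 − r) + C, and the shift is the gap in proportions times c. For a 20-point gap:

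- level only: c = 0.5 × 0.5 = 0.25; shift 0.2 × 0.25 = 0.05 SD
- change only: c = 0.5; shift 0.2 × 0.5 = 0.10 SD
- both: c = 0.25 + 0.5 = 0.75; shift 0.2 × 0.75 = 0.15 SD

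**3. Standard error.** For one pairwise contrast with baseline adjustment and medication irrelevant, SE = √(2/20) × √(1 − r²) = 0.316 × 0.866 = 0.274 SD. If medication matters and is left out, the residual variance rises from 0.75 to 0.75 + c²·p(1 − p). With p = 0.3, p(1 − p) = 0.21:

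- level only: 0.316 × √(0.75 + 0.0625 × 0.21) = 0.276
- change only: 0.316 × √(0.75 + 0.25 × 0.21) = 0.283
- both: 0.316 × √(0.75 + 0.5625 × 0.21) = 0.295

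The shifts in step 2 are therefore about 0.05/0.276 = 0.18, 0.10/0.283 = 0.35 and 0.15/0.295 = 0.51 of a standard error.

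**4. Gain and cost of adjusting.** Relative to 0.274, the standard error avoided is about 1%, 3% and 7% in the three cases. The extra term itself costs about 1/(2 × 56) = 0.9%, where 56 = 60 − 4 is the residual degrees of freedom of a single-time model with intercept, two group terms and baseline. The net gain is then roughly nil, 2% to 3%, and 6%. Simulation agrees: with three arms of 20, the SD of the contrast went from 0.275 to 0.277 when medication was irrelevant, from 0.289 to 0.281 for change only, and from 0.296 to 0.278 for both. In a two-arm simulation with level only it was 0.285 without the term and 0.287 with it.

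**5. Effect of stratified blocks.** With separate permuted-block lists for users and non-users, every complete block is balanced, so only the last incomplete block can differ. The gap in users is then at most 1 with blocks of 3 and at most 2 with blocks of 6 (block sizes assumed).

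**The case against.** The strongest reply is that the plan already deals with the main route. Users must be stable and intend to stay so, women expecting a medication change are excluded, and baseline outcome is in every model. A constant drug effect on level is largely handled, and an effect on change is supported by nothing in the documents. The usual standard error already allows for chance imbalance. Not stratifying a 60-woman trial is a legitimate choice, and a case could be made for other covariates. All of this stands, and it is why the point is small. It does not remove the reason for preferring this covariate: the protocol itself singles out bladder medication in its eligibility rules, and the value is already collected.

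Three stronger readings are tempting, and the documents do not support them.

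- A reader might infer that the protocol ties OAB drugs to prefrontal function. It ties down-regulation of the PFC to non-response to drug treatment. That an enrolled user who still leaks is such a non-responder is an inference. An untreated woman may equally be a past non-responder who stopped, so current use is an imperfect marker.
- A reader might extend the argument equally to cue-provoked urgency and Stroop reaction time. The protocol's background says that conditioned responses are rarely reduced by drugs, which weakens the case for Aim 3.
- A reader might conclude that arm effects could not be told apart from drug background. Randomisation keeps the contrast unbiased on average, and a table of use by arm would show any gap.

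**Conclusion.** The point holds as a minor, optional improvement to the Aim 2 analysis. Medication status is available and possibly prognostic, and it goes unused. What is at stake is a net precision gain of between nothing and about 6%, and protection against one unlucky allocation. Such an allocation would move a contrast by about 0.05 to 0.15 SD for a 20-point gap, less than or about half a standard error. The chance of a gap that large is substantial only if use is fairly common: 40% to 51% for some pair of arms at 25% to 50% use, but 15% at 10% use. Prevalence, the 0.5 SD effect and the correlation of 0.5 are all assumptions. The omission does not bias the trial, and the documents do not show that medicated women respond differently to tDCS.

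**What to change.** Add one sentence to the SAP: baseline OAB medication (yes/no) enters each Aim 2 model as a fixed covariate, and its frequency is tabulated by arm. For Aim 3, add it only in a sensitivity analysis. If randomisation is still open, the 1:1:1 blocked list could be run separately for users and non-users; this is optional.

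Report arm-by-medication estimates as descriptive only. A main-effect covariate does not address a different response to tDCS. At 25% to 50% use there would be about 5 to 10 users per arm (15/3 to 30/3), too few to test one.

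The cost is one degree of freedom, about 1% of precision or less if medication is irrelevant, and, with stratified lists, possibly one extra incomplete block. No eligibility or treatment rule changes.

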Mindfulness + tDCS to reduce urgency incontinence in women

NCT# 04652869

Primary Outcomes: Data Analysis Plan

9/13/2022

Primary Outcomes: Data Analysis Plan. Prior to hypothesis testing, descriptive statistics and graphic displays will be used to identify outliers, missing data, and patterns of attrition, and to guide transformations and appropriate tests. The primary analyses will be evaluated via mixed model regressions with Bonferroni post-hoc comparisons. Mixed model regression features advantages over traditional regression due to the ability to handle repeated assessments of both predictor variables and outcome variables. For **Aim 1**, We will assess feasibility as >85% study completion, acceptability as a score ≥ 50 on 8-item post-study survey rating (scale 0-100), and mindfulness compliance as an average rating ≥ 75 on the compliance survey (scale 0-100). We will use chi-square to assess attrition differences between groups, and one-way ANOVA to assess differences in acceptability and compliance ratings. For **Aim 2**, mixed model regressions will test the main effects of experimental group (1=MI, 2=tDCS, and 3=MI+tDCS) on ICIQ-FLUTS score (pre, post, and follow-up), UUI episodes, and urgency survey scores (3-day mean score at baseline, last three days before re-test, and last 3-days of follow-up) as dependent variables. Pre-intervention (baseline) levels of each dependent variable will be entered as a covariate in respective regression models. This process will be repeated for **Aim 3**, with separate models evaluating treatment effects on Stroop RT and cue-provoked urgency. For Stroop RT, the primary dependent variable will be post-test minus pre-test change. For cue-provoked urgency, the primary dependent variable will represent a double-difference score of urgency minus safe cues, and post-test minus test.

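### H2 claims that MI+tDCS beats both single treatments, but the SAP names only a three-level group effect with an undefined Bonferroni step and no rule for which result supports H2

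*SAP*

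**What the plan says.** The protocol's Study Objectives state H2 twice. For Aim 2: "MI + tDCS will lead to the greatest reduction in these UUI symptoms". For Aim 3: "MI + tDCS will lead to greater reductions in these measures relative to either MI or tDCS alone". Both are directional and set in advance, and both require the combined arm to be better than each of the other two.

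The SAP (Primary Outcomes: Data Analysis Plan, repeated in the protocol under the same heading) gives the general method: "The primary analyses will be evaluated via mixed model regressions with Bonferroni post-hoc comparisons". For Aim 2, "mixed model regressions will test the main effects of experimental group (1=MI, 2=tDCS, and 3=MI+tDCS"), with the baseline value as a covariate. Aim 3 repeats the process on change scores.

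On size, the protocol's Procedures and Protocols section says "Sixty women will be recruited from the Pitt+Me online registry" and plans "to randomize subjects in a 1:1:1 ratio", so about 20 per arm.

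Neither document says:
- which result would count as support for H2;
- which pairs, outcomes or time points form the Bonferroni family;
- whether the pairwise step depends on a significant group effect;
- the alpha, its sidedness, an effect size, an SD or a target power.

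**The concern.** The hypothesis and the named test ask different questions. A group effect with 2 degrees of freedom responds to any difference among the three arms, including differences that contradict H2. The pairwise step is closer to H2, but it is described only as post-hoc with an undefined family, so the analyst must decide afterwards which comparisons count and at what level.

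Two things are at stake. First, with no decision rule, a significant group effect or one winning comparison could be reported as support for H2. Secondly, if Bonferroni is applied in the usual way over all three pairs, a trial of about 20 per arm gives up power on H2 for a correction that the joint claim does not require.

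**Working it through.** **Inputs from the documents.** N = 60 and 1:1:1 allocation give 20 per arm. The 85% completion target in Aim 1 gives 0.85 × 20 = 17 completers per arm; it is a feasibility target, used here only as a lower case.

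**Assumptions.** Alpha 0.05 two-sided; normal errors with a common residual SD; one outcome at one time point; d is a difference in baseline-adjusted residual SD units, shown from 0.5 to 1.0. The plan gives no power figure to reproduce.

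**Step 1: the group effect when H2 is false.** Take means of 0 (MI), d (tDCS) and d (MI+tDCS). The combined arm does not beat tDCS, so H2 is false. The F test has 2 and 3(n−1) degrees of freedom, with noncentrality n × (2/3)d².
- n = 20, d = 0.8: noncentrality 20 × 0.667 × 0.64 = 8.53; critical F(2, 57) = 3.16; rejection rate 72%.
- n = 17, d = 0.8: 64%.
- n = 20, d = 0.5: 34%.

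In the n = 20, d = 0.8 case, MI+tDCS also wins at least one pairwise comparison at 0.05/3 in 53% of trials. A single winning contrast is therefore not evidence for H2 either.

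**Step 2: error rate of a joint rule.** To claim that MI+tDCS beats both arms, both nulls must be rejected (an intersection-union test). If either null is true, the chance of rejecting both in the right direction cannot exceed the chance of rejecting the true one in that direction, which is 0.05/2 = 2.5%. Simulation with n = 20 and means 0, 0.8, 0.8 gives about 2.4%. With both tests at 0.05/3 the ceiling is 0.05/6 = 0.8%, and simulation gives 0.8%.

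**Step 3: power to win both contrasts.** MI+tDCS exceeds each single arm by d, and the single arms are equal. Each t statistic has noncentrality d√(n/2); at d = 0.8 and n = 20 this is 0.8 × √10 = 2.53. With 57 df the two-sided critical values are 2.00 at 0.05, 2.30 at 0.05/2 and 2.47 at 0.05/3. The two contrasts share the combined arm, so the joint probability was simulated (200,000 trials per case).

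| n per arm | d | Each at 0.05 | Each at 0.05/2 | Each at 0.05/3 |
|---|---|---|---|---|
| 20 | 0.5 | 19% | 12% | 9% |
| 20 | 0.6 | 30% | 20% | 16% |
| 20 | 0.8 | 56% | 43% | 37% |
| 20 | 1.0 | 80% | 69% | 63% |
| 17 | 0.8 | 47% | 35% | 29% |

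The last column applies if Bonferroni covers all three pairs, the usual reading for a three-level factor. The 0.05/2 column applies if it covers only the two H2 contrasts.

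**Step 4: several outcomes.** H2 covers five outcomes. Three (ICIQ-FLUTS, UUI episodes, urgency survey) are assessed both post-training and at follow-up; two (Stroop RT, cue-provoked urgency) post-training only. That is 3 × 2 + 2 = 8 possible H2 tests. If all were independent (an assumption) and each at its worst case, the chance of at least one false H2 claim would be 1 − 0.975⁸ = 18% at 2.5% each, against 1 − 0.992⁸ = 6% at 0.8% each.

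**The case against.** The strongest reply is that the plan pairs the group effect with adjusted pairwise comparisons, and that no sentence says a significant group effect establishes H2. A reader might infer from the 72% that the planned analysis will endorse H2 when it is false. The documents do not support that. If H2 were declared only when both Bonferroni comparisons succeed, false claims would stay at or below about 0.8%. The gap is the missing decision rule.

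A reader might also conclude that Bonferroni buys nothing. It does: the ceiling is 0.8% rather than 2.5% per outcome, and Step 4 shows that this matters if many outcomes are tested without a lead one. The correction is unnecessary only for the joint claim on one outcome at one time point. Bonferroni is valid and conservative, so this part is about efficiency, not a wrong test. It is also not clear that the planned Bonferroni step covers outcomes or time points at all.

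Two further inferences fail. The 56% and 37% are not properties of this trial, because the documents give no effect size or alpha and do not define the family. And H2 is not the only question answered by comparing randomised arms: Aim 1 compares attrition, acceptability and compliance between groups, and the design section sets out to examine independent as well as combined effects. MI versus tDCS therefore has a legitimate place among the comparisons, though not in H2.

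**Conclusion.** The concern holds in this limited form. H2 is a pre-stated claim of superiority over both single treatments, and the SAP does not connect any test result to it. The group effect is not a test of H2, and the Bonferroni family is undefined.

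Under two-sided 0.05 and 20 per arm, adjusting over three pairs costs about 10 percentage points of power for H2 at d = 0.5, 19 at d = 0.8 and 17 at d = 1.0. Adjusting over the two H2 contrasts costs 13 points at d = 0.8. The direction of the loss does not depend on d; its size does. This is a worthwhile, low-cost improvement to the plan rather than correction of an invalid analysis.

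**What to change.** Amend the SAP as follows.

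1. For each outcome, name the time point at which H2 is judged, for example post-training, with follow-up secondary.
2. Test H2 by two planned contrasts from the baseline-adjusted model with group as a three-level class factor: MI+tDCS minus MI, and MI+tDCS minus tDCS.
3. Call H2 supported for that outcome only if both contrasts favour MI+tDCS at two-sided p < 0.05. Report both estimates with 95% confidence intervals.
4. State that neither a significant group effect nor a single winning contrast supports H2.
5. Keep a multiplicity adjustment for MI versus tDCS and for any claim resting on one contrast. Either Bonferroni with its family defined, or the three-arm closed test (group F at 0.05, then the pair at 0.05) at that one time point, would serve.
6. Name one lead outcome for H2 in each aim, or label the remaining results as unadjusted across outcomes.

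This changes wording only and needs no new data or participants. It has two costs: H2 cannot be claimed from one winning contrast, and the per-outcome false-claim ceiling is about 2.5% rather than the 0.8% that three-pair Bonferroni with both wins required would give.

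### Does a bare 85% in the Aim 1 objective conflict with the strict >85% feasibility rule in the analysis plan?

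*SAP*

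**What the plan says.** Feasibility appears in three places.

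- **Protocol, Study Objectives, Aim 1 H1:** "Feasibility: 85% of all enrolled participants will complete the study". A percentage and a denominator are given, without an inequality sign.
- **SAP, Primary Outcomes: Data Analysis Plan, Aim 1:** "We will assess feasibility as >85% study completion". The inequality is strict and no denominator is named.
- **Protocol, Primary Outcomes: Data Analysis Plan, Aim 1:** the same sentence as the SAP, again strict and without a denominator.

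The other two Aim 1 criteria, acceptability (50 on a 0-100 scale) and mindfulness compliance (75 on a 0-100 scale), carry an inclusive sign (≥) in all three places.

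On numbers, the protocol's Procedures and Protocols section says "Sixty women will be recruited". It then describes telephone screening, consent, further screening and a cue interview, after which "Participants will then be randomized to one of 3 groups". The word enrolled is not defined. Neither document turns 85% into a count of women.

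**The concern.** A target stated as a bare 85% is naturally read as at least 85%. The analysis text asks for more than 85%. Usually the two amount to the same thing, but 85% of 60 is a whole number, so at the planned size the inequality sign decides one result. Feasibility is the first criterion of Aim 1 and is judged against a threshold. With two forms of that threshold in print, a trial ending with 51 completers out of 60 could be described either way once the data were known. The inclusive sign on the neighbouring criteria makes the strict sign on feasibility look unintended.

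The denominator raises a second question. The objective counts all enrolled women and the analysis sentence names no group. Because consent comes before randomisation, enrolled could mean either stage, and women lost between the two would count against feasibility under one meaning only.

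**Working it through.** The documents state no pass count or power figure for feasibility, so there is nothing to reproduce first.

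**Inputs.** Threshold 85% (Study Objectives; both analysis sections). Planned recruitment 60 (Procedures and Protocols). Two assumptions are needed for a conflict to arise: that the bare 85% means at least 85%, and that the denominator is 60.

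**Pass counts.** 0.85 × 60 = 51 exactly.

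| Completers of 60 | Percentage | At least 85% | More than 85% |
|---|---|---|---|
| 50 | 83.3% | not met | not met |
| 51 | 85.0% | met | not met |
| 52 | 86.7% | met | met |

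The readings differ at 51 and nowhere else.

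**Other denominators.** Since 0.85 = 17/20, 0.85 × N is a whole number only when N is a multiple of 20. At any other N both readings need the same count:

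- N = 55: 46.75, so both need 47.
- N = 59: 50.15, so both need 51.
- N = 61: 51.85, so both need 52.

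Between 50 and 80, only N = 60 and N = 80 separate them.

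**Chance that it matters, given N = 60.** If each woman completes independently with probability p, the two chances of passing differ by P(X = 51) = C(60, 51) × p^51 × (1 − p)^9. The documents give no expected p, so a range is shown.

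| Assumed p | P(X ≥ 51) | P(X ≥ 52) | P(X = 51) |
|---|---|---|---|
| 0.80 | 0.213 | 0.127 | 0.086 |
| 0.85 | 0.588 | 0.445 | 0.143 |
| 0.90 | 0.927 | 0.858 | 0.069 |
| 0.95 | 0.999 | 0.997 | 0.002 |

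The largest value over all p is 0.143, at p = 0.85 = 51/60.

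**What the data would show.** Exact (Clopper-Pearson) 95% intervals are 73.4% to 92.9% for 51/60 and 75.4% to 94.1% for 52/60. A reader would draw the same conclusion about completion from either.

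**Which text governs.** The objective is a hypothesis about what will happen. The analysis sentence is the only statement of how feasibility will be judged, and it is the same in the protocol and the SAP. Followed as written, it gives 52 or more of 60. The objective does not say that exactly 85% passes, so the analysis sentence makes it precise without contradicting it.

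**The case for a change.** The strongest case for an edit is that the planned size is one of the few at which the sign matters. At a true completion rate of 85%, the chance of declaring feasibility is 0.588 under one reading and 0.445 under the other. A pass/fail criterion should have its count settled before data are seen. The inclusive signs on the other two criteria survive in the same sentence, so a PDF-reading fault is an unlikely explanation. The edit would also cost only a phrase.

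Part of this stands. The wording does differ, the arithmetic is right, and reading the objective as at least 85% is natural. The claim that the count is unsettled does not stand, because the analysis text fixes it, and fixes it identically in both documents. The gap between 0.588 and 0.445 is the chance of exactly 51 completers at the least favourable completion rate. It also assumes a denominator of exactly 60, which the documents do not guarantee: sixty is a recruitment figure, and screening and consent come before randomisation.

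The denominator point is fair as far as it goes. It could move the required count by more than one, since the count rises with the number of women included. But it is missing detail, and the sections do not contradict each other: the objective for the same aim names all enrolled women, and an analyst would carry that into the analysis sentence. How many women might consent without being randomised is not stated, so no size can be put on the effect. Reporting completion from both consent and randomisation, with an exact interval, is good practice but corrects no wrong result.

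**Conclusion.** No change to the plan is needed. The difference is a looser phrase in an aims statement beside a precise rule in the analysis text, and the analysis text gives one sound answer: 52 or more completers if the denominator is 60. A conflict needs an at-least reading of a sentence that does not contain those words, a denominator of exactly 60, and exactly 51 completers. Given that reading and denominator, its chance is at most 14.3%, falling to 8.6% at 80% true completion, 6.9% at 90% and 0.2% at 95%. These figures assume independent completion. Even then, one label on a descriptive target would change, the interval estimates would hardly move, and no continuation decision or hypothesis test in the documents depends on it. Using the same sign in the objective would be a clerical tidy-up. The undefined term enrolled is a gap that analysts can fill sensibly by stating, when they report completion, which women they counted.
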